5.2. Secondary Aim

Aim 2. To examine mediators of the impact of the intervention. Hypothesis. The effects of the intervention on SSE and sun protection behaviors will be mediated by melanoma knowledge, self-efficacy for SSE and sun protection behaviors, perceived benefits of SSE and sun protection behaviors, perceived benefits of SSE and sun protection behaviors, perceived benefits of SSE and sun protection behaviors, and perceived controllability of melanoma. For each potential mediator, the four component steps (Frazier et al., 2004; Mallinckrodt et al. 2006) will be examined via logit models (for the SSE outcome) and linear models (for the sun protection behaviors outcome). Using Krull and colleagues' approach for multilevel models (Krull & Mackinnon, 2001), we will calculate the product of the two pieces of the mediating path (from intervention group assignment to mediating variable and from mediating variable to outcome), with the outcomes at 24 weeks as the primary focus (and 48 weeks outcomes examined secondarily). Bootstrap procedures will be utilized to formally test for significance of the mediating pathway (Mallinckrodt et al. 2006; Shrout & Bulger, 2002). Imputation will be used to evaluate the robustness of the results to missing data, assuming dropouts are MAR as well as MNAR.

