3.6. Sample Size

Up to 30 individuals will take part in Phase 1 of the project. For Phase 2 of the project, we will recruit 420 participants. For Phase 3 of the project, we will recruit up to 50 participants. For the Phase 2 RCT study,

we conducted power calculations for the primary and secondary aims. (We did not conduct power calculations for Aim 3 because it is an exploratory aim.) For the primary aim (intervention efficacy), there are two primary outcomes: engagement in thorough SSE (binary outcome) and sun protection behavior index (continuous score) at 24 weeks post-baseline. At baseline, we anticipate that 9% of participants will be adherent to thorough SSE. Based on our own and others' prior research (Glanz et al., 2010; Janda et al., 2011; Manne et al., 2010; Weinstock et al., 2007), we anticipate that the rate of adherence to thorough SSE at 24 weeks post-baseline will be ≥35% in the ITW group and this will be at least 15 percentage points higher than the adherence rate in the Usual Care group. An increase in SSE of this magnitude would be considered a successful rate. We assume proportions of individuals completing SSEs are compared between treatments using a z-test. Allowing for 10% dropout at 24 weeks (a rate comparable to that experienced in our prior research; Manne et al., 2010) and an adherence rate to thorough SSE of up to 20% in the Usual Care group at 24 weeks post-baseline (which is at the upper end of what might be expected), 153 individuals would need to be recruited in each group to obtain 80% power. Power calculations for the sun protection behaviors outcome are based on results of prior tailored interventions, including our own (Glanz et al., 2010; Manne et al., 2010). In our prior RCT, sun protection scores at baseline were 2.8 for both groups and increased to 3.2 and 3.4 for the generic and tailored interventions, respectively. Given that the Usual Care control group in the current RCT is not an active control (the generic intervention in the prior study was an active control), we assume that the sun protection scores in that group would increase to a maximum of 3.0. Standard deviations were, on average, 0.66 at baseline and 0.76 at follow-up. We assume a correlation between baseline and follow-up measures of 0.60. Under these assumptions, recruiting 153 individuals to each group would provide more than 80% power to detect differences in changes in sun protection scores from baseline to 24 weeks post-baseline. For the secondary aim (intervention mediators), we utilized sample size tables for mediated effects based on simulation studies that model the two pieces of the mediating path (from intervention group assignment to mediating variable and from mediating variable to outcome) (Fritz & Mackinnon, 2007). Based on the results of relevant prior research, we conservatively assume that one of the two paths will have a regression coefficient of at least .14 (a small effect, according to Cohen's [1998] criteria) and the other will have a regression coefficient of at least .26 (a small-to-moderate effect). Under those assumptions, and allowing for 10% dropout at 24 weeks, recruiting 210 individuals to each group would provide 80% power to detect mediational effects (Fritz & Mackinnon, 2007). Overall, based on a consideration of the aforementioned factors, we will recruit 210 individuals to each of the ITW and Usual Care groups, for a total sample size of N = 420, which will provide at least 80% power for the primary and secondary aims. We anticipate that at least 378 of the 420 patients (i.e., 90%) will complete the 24 weeks post-baseline assessment and 357 (85%) will complete the 48 weeks post-baseline assessment.

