4.2. Phase 2 Measures

An overview of the study measures is shown in Table 1. We will utilize concise, psychometrically valid measures used in our prior research or that of other research groups.

	Baseline	FU 1	FU 2	FU 3
Background Variables and Correlates				
Clinical characteristics	✓			
Internet experience	✓			
Sociodemographic factors	✓			
Melanoma risk factors	✓			
Receipt of TCE	✓	✓	✓	✓
Receipt of biopsy, skin cancer diagnosis		✓	✓	✓
Distress about melanoma	✓	✓	✓	✓
Worry about melanoma recurrence	✓	✓	✓	✓
Perceived controllability of melanoma	✓	✓	✓	✓
Melanoma knowledge	✓	✓	✓	
Perceived severity of melanoma	✓	✓	✓	
Perceived risk of melanoma recurrence	✓	✓	✓	
SSE self-efficacy	✓	✓	✓	
SSE benefits and barriers	✓	✓	✓	
SSE norms	✓			
Physician SSE recommendations	✓			✓
Sun protection self-efficacy	✓	✓	✓	
Sun protection benefits and barriers	✓	✓	✓	
Sun protection norms	✓			
Automaticity of sun protection behaviors		✓	✓	✓
Physician sun protection recommendations	✓			✓
Outcome Variables				
SSE	✓	✓	✓	✓
Sun protection behaviors	✓	✓	✓	✓
Healthcare provider visits		✓	✓	✓
Intervention Evaluation and Usage				
Impact and effectiveness of the intervention		✓		
Evaluation and utility of the intervention		✓		
Website usage		✓	✓	✓

Note. TCE = total cutaneous examination; SSE = skin self-examination; FU = follow-up; FU 1 = 8 weeks post-baseline; FU 2 = 24 weeks post-baseline; FU 3 = 48 weeks post-baseline.

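### The mediation models in Section 5.2 specify neither baseline adjustment nor the mediator's survey wave, so a true effect on the mediator can be mistaken for mediation

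*Combined protocol and SAP*

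**What the plan says.** Section 5.2 takes each candidate mediator in turn. The component steps "will be examined via logit models (for the SSE outcome) and linear models (for the sun protection behaviors outcome". The indirect effect is then formed: "we will calculate the product of the two pieces of the mediating path". Testing is by bootstrap: "Bootstrap procedures will be utilized to formally test for significance of the mediating pathway". Timing is given for the outcome only, "with the outcomes at 24 weeks as the primary focus (and 48 weeks outcomes examined secondarily". No wave is given for the mediator, and no covariate is named in either path. Imputation is planned, but it addresses dropout.

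Table 1 in Section 4.2 defines the waves: "FU 1 = 8 weeks post-baseline; FU 2 = 24 weeks post-baseline; FU 3 = 48 weeks post-baseline". Every mediator named for Aim 2 is collected at baseline, 8 weeks and 24 weeks; only perceived controllability is also collected at 48 weeks. SSE and sun protection are collected at all four waves.

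Other sections do not fill the gap. The covariate adjustment in Section 5.1 is an Aim 1 sensitivity analysis for demographics that differ at baseline. The change-over-time models in Sections 5.1 and 5.3 are not applied to the mediation paths.

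Section 3.6 sizes the trial partly on this aim. It assumes that "one of the two paths will have a regression coefficient of at least .14" and "the other will have a regression coefficient of at least .26", and concludes that, "allowing for 10% dropout at 24 weeks, recruiting 210 individuals to each group would provide 80% power to detect mediational effects".

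**The concern.** Aim 2 asks why the intervention works. The indirect effect is a × b, where a is the effect of group on the mediator and b is the association of mediator with outcome given group. Randomisation makes a causal. It does nothing for b, which is observational.

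**Baseline confounding.** Someone who enters with high sun protection self-efficacy and good sun protection will tend to have both at follow-up. Without the baseline values in the model, b picks that up. If the intervention also raises self-efficacy, a × b is non-zero and the bootstrap reports mediation, even if self-efficacy has no effect on behaviour.

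**Temporal order.** The plan permits mediator and outcome to come from the same 24-week survey. The primary SSE outcome refers to the most recent check within the preceding two months (Section 4.2.2), so the behaviour can precede the mediator report. Doing the behaviour may raise confidence in doing it, and b would then run backwards.

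The trial could name mediators that do not mediate. Those would be the components carried into later versions of the website. The aim is also not incidental to the design: it raised recruitment from 153 to 210 per group.

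**Working it through.** **Inputs from the documents.** 420 recruited and 10% dropout, so N = 420 × 0.90 = 378; paths .14 and .26; baseline-to-follow-up correlation 0.60 (Section 3.6, stated for sun protection only); 9% thorough SSE at baseline; 20% versus 35% at 24 weeks.

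**Assumptions not in the documents.** Two-sided 0.05; stability 0.6 for mediators too; baseline mediator-outcome correlation r of 0.2 to 0.4; the .14 and .26 read as standardised coefficients. A joint-significance test (both paths significant) stands in for the bootstrap.

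**Step 1: reproduce the plan's power.** √378 = 19.44. For a standardised coefficient c, power ≈ Φ(19.44c − 1.96).
- .14: Φ(2.72 − 1.96) = 0.777
- .26: Φ(5.06 − 1.96) = 0.999
- joint: 0.777 × 0.999 = 0.776

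Simulated percentile and bias-corrected bootstraps give 0.790 and 0.818, against the stated 80%. The plan's figure reproduces on the standardised scale.

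**Step 2: no true mediation, observed baseline scores carry all the confounding.** Each follow-up score is 0.6 × its baseline score plus noise, and the mediator has no effect on the outcome. The unadjusted coefficient is then b = 0.6 × 0.6 × r = 0.36r. The false-mediation rate is about power(a) × power(b).

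| r | spurious b | 19.44b | power(b) | a = .14 | a = .26 | simulated |
|---|---|---|---|---|---|---|
| 0.2 | 0.072 | 1.40 | 0.288 | 0.22 | 0.29 | 22–28% |
| 0.3 | 0.108 | 2.10 | 0.556 | 0.43 | 0.56 | 46–58% |
| 0.4 | 0.144 | 2.80 | 0.799 | 0.62 | 0.80 | 62–79% |

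With baseline mediator and baseline outcome in the models, the simulated rate is about 4–6% and mean b is 0.00.

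**Step 3: a stable trait measured imperfectly at every wave.** Let c be the mediator-outcome correlation at any pair of waves. Unadjusted, b = c. Adjusted for both baseline scores, the normal equations give b = 0.4c / (1.6 − 2c²).
- c = 0.2: 0.08 / 1.52 = 0.053
- c = 0.4: 0.16 / 1.28 = 0.125

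Adjustment shrinks b to about a quarter or a third of its unadjusted size but does not remove it. For c of 0.2 to 0.4, the simulated rates are about 77–100% unadjusted and about 17–67% adjusted. The mediator wave makes no difference to this bias: at c = 0.18 and a = .14, the unadjusted rate is 73% with either the 8-week or the 24-week mediator.

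**Step 4: the intervention does not move the mediator (a = 0).** The unadjusted rate stays at or below about 5–6%, and mean a × b is about 0.

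**Step 5: reverse causation alone.** Here the 24-week outcome feeds the 24-week mediator (assumed coefficient 0.2 to 0.3), the intervention has an assumed direct effect of 0.4 SD on the outcome, and baseline scores are adjusted for.

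| mediator wave | a = 0 | a = .14 |
|---|---|---|
| 24 weeks (same survey) | 17–28% | 96–99.6% |
| 8 weeks | 0.1–0.3% | 5–6% |

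The same-survey rate is raised even at a = 0, because the intervention reaches the 24-week mediator through the behaviour.

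**Step 6: binary thorough SSE.** Repeating Step 2 with 9% adherent at baseline and 20% versus 35% at 24 weeks gives about 13–17%, 26–35% and 43–53% unadjusted for r of 0.2, 0.3 and 0.4.

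**The case against.** The strongest reply is that Section 5.2 is silent on covariates and waves but does not rule them out, and that it defers to cited mediation methods. That is fair as to wording: the defect is that nothing is specified, not that adjustment is forbidden. But models fitted as written would have the open path, and no other section closes it.

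Several stronger readings are tempting and are not supported.

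- *Baseline traits alone produce a non-zero product.* They do not. Randomisation keeps a at zero unless the intervention moves the mediator (Step 4). False mediation through this route needs a real effect on the mediator, which Aim 2 expects.
- *Baseline adjustment restores the nominal error rate in every case.* It does so only if the observed baseline scores carry all the confounding (Step 3).
- *Choosing the 8-week mediator cures the baseline confounding.* It does not. It addresses reverse causation only.
- *The headline rates apply to SSE.* They come from a linear outcome. For binary SSE they are smaller, and with 9% adherent at baseline the baseline outcome may add little; the baseline mediator matters most.

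Two further points stand. If .14 were an SD difference on a 0/1 group indicator, the standardised path would be .07, and the Step 2 rates at that path would be 8%, 15% and 22%. On that reading, however, the stated 80% power would be only about 27–31%. And for 48-week outcomes the design already forces an earlier mediator, except for perceived controllability, so the same-survey problem is largely confined to 24 weeks.

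**Conclusion.** The concern holds as two distinct gaps in a secondary aim.

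The missing baseline adjustment leaves the mediator-to-outcome path confounded. Given an intervention that moves the mediator, false mediation is found in about 22–79% of simulated trials where observed baseline scores carry the confounding, and in about 77–100% where a stable trait lies behind them. Adjustment brings these to about 4–6% and about 17–67% respectively. The unadjusted model is the worse one throughout.

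The open mediator wave is a separate reverse-causation problem, largely removed by taking the mediator at 8 weeks.

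The sizes depend on assumed mediator-outcome correlations, on carrying the 0.60 stability over from sun protection to the mediators, on standardised path coefficients, and on a joint-significance test in place of the bootstrap. They apply most directly to the sun protection index. The direction of the bias does not depend on those values, provided the baseline mediator and the behaviour are positively related. A reader might infer that the mediation power statement or the treatment comparison is also wrong; the power figure reproduces, and Aim 1 is unaffected. This should be corrected before the Aim 2 analysis.

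**What to change.** Amend Section 5.2 to state:

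1. **Wave.** The 8-week mediator for 24-week outcomes, and the 24-week mediator for 48-week outcomes. The latter is already the latest available for every mediator except perceived controllability.
2. **Covariates.** In both component models, the baseline value of that mediator, the baseline value of the outcome, and the stratification factors (disease stage and time since diagnosis).
3. **Residual confounding.** A prespecified sensitivity analysis showing how strong a remaining mediator-outcome association would have to be to remove the indirect effect. A change-score analysis could accompany it: in the stable-trait simulations with c of 0.18 and 0.30 it held false mediation at about 4–5%, though that result is specific to that model.
4. **Same-survey analyses.** Reported as sensitivity or descriptive results, not as the main test of mediation.

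The cost is a few sentences of text. Table 1 already schedules every measurement needed, and Section 3.2 expects the modules to be opened and worked through in the first weeks, so week 8 should normally follow exposure. The downside is a possible small loss of power, because an 8-week mediator may correlate somewhat less with a 24-week outcome.

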5.3. Exploratory Aim

Aim 3. To examine moderators of the impact of the intervention. Research Question. To evaluate whether ITW effects are moderated by the following factors: time since diagnosis; disease stage; age; sex; income; education; Internet experience; distress about melanoma; worry about recurrence; and evaluation and usage of the ITW. To examine this aim, we will incorporate interactions between the effect of intervention and potential moderators into the multilevel models described for Aim 1, with the outcomes at 24 weeks as the primary focus (and 8 week and 48 week outcomes examined secondarily). In order to minimize the significance due to multiple testing, variables with low variability in the sample will be eliminated from consideration, and Hochberg's step-down procedure for multiple testing will be employed for the remaining candidates for moderators. Again, imputation will be used to evaluate robustness of the results to missing data, assuming dropouts are MAR as well as MNAR.

Additional Analyses. Using the same analytic approach as for Aim 1, we will examine the impact of the intervention on the number of health care visits. We will use multilevel models similar to those described in Aim 1 to compare changes from baseline to follow-up in distress about melanoma, worry about melanoma recurrence, and perceived risk of melanoma recurrence for the ITW and Usual Care groups. Descriptive statistics, including means and standard deviations or relative frequencies will be used to summarize the indicators of study feasibility (ineligibility rate/reasons, recruitment rate/reasons for refusal, differences in sociodemographic and medical factors between study decliners and those recruited, dropout rate and reasons, and use of the intervention website). Additionally, we will use chi-square and regression analyses to examine retention rates and usage of the ITW vary according to patient income and education.

6. Data and Safety Monitoring

This is a minimal risk study and thus does not require a formal data and safety monitoring plan. As outlined in Section 4.4., appropriate safeguards are in place to manage the potential risks of the study. Databases for participant recruitment and tracking, medical records review data, and participant survey data will be developed and maintained by the CINJ Population Science Research Support Core using HIPAA-compliant DatStat software. Approval for use of this software in research studies has been provided by the Rutgers Biomedical and Health Sciences Institutional Review Board (IRB). (The approval process included: obtaining a Technology Professional Service Agreement and a Business Associate Agreement from DatStat; the approval of a Security Questionnaire from the Rutgers Office of Information Technology; and the completion of a Security Risk and Assessment Tool by the Rutgers

Protocol Version Date: 4/5/22

CINJ Office of Information Technology.) The software allows for research study personnel to be assigned data access and privileges specific to their role on the study.

DatStat secure servers are registered with site certificates provided by AddTrust that provide for advanced encryption over the wire. As each user moves through the survey form, his/her responses are encrypted while in-transit between the browser and DatStat's server using SSL (Secure Sockets Layer) and 40, 56, or 128-bit Public Key Encryption. All servers used for data collection are highly fault-tolerant and equipped with redundant, hot-pluggable power supplies, redundant network interfaces, and RAID 5 hot-swappable disk storage. All primary servers are plugged into a monitored, uninterruptible power supply (UPS). DatStat servers are stored in a locked server cabinet/rack, which are housed in a state-of-the-art, well-ventilated data center. Physical access to servers and data backup is restricted to a minimal number of information technology professionals. The servers are secured with physical and firewall security.

The study principal investigator and co-investigators will provide oversight with regard to monitoring the study. All adverse/unexpected events will be reported in line with Rutgers Biomedical Health Sciences IRB and Rutgers CINJ Office of Human Research Services (OHRS) guidelines. As part of its internal audit program, the OHRS at Rutgers CINJ will monitor accrual to the study and adherence to the overall protocol, verify the completion of informed consent forms, and ensure that data collection and storage procedures are being followed appropriately.

7. Reporting Results

The policies and procedures of Rutgers University's legal department (see: Investigator's Handbook) will govern publication of the results of this trial. The results of this trial will be submitted for publication in a timely manner following its conclusion. The Rutgers Cancer Institute of New Jersey PI and all co-authors will review any abstract of manuscript prior to its submission.

8. Bibliography

American Cancer Society. Cancer facts and figures, 2011. Atlanta, GA: American Cancer Society.

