Aim 3 (exploratory aim): To examine moderators of the impact of the intervention. Research Question. To evaluate whether ITW effects are moderated by the following factors: time since diagnosis, disease stage, age, sex, income, education, Internet experience, distress about melanoma, worry about recurrence, and evaluation and usage of the ITW.

2. Background and Significance

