3.2. Phase 2: RCT of the Efficacy of the Intervention

Consented patients will be provided with a link to a secure, password-protected website to complete a baseline survey. After completing the survey online, patients will automatically be randomized to the ITW or Usual Care condition. Patients will be stratified according to disease stage and time since diagnosis (3–<14 months vs. 14–24 months) and then, within strata, block randomized using blocks of four or six patients. The study biostatistician, [name], was responsible for creating the randomization schedule and overseeing the randomization process, following standard operating procedures of the Rutgers CINJ Biometrics Shared Resource. After 8 weeks, study participants will be prompted (via email, as well as by telephone, text message [with their permission] and mail, as necessary) to complete an online survey (follow-up 1), followed by additional online surveys 24 weeks (follow-up 2) and 48 weeks post-baseline (follow-up 3). The estimated time to complete each online survey varies from 40 minutes for the baseline to 20 minutes for the follow-up 3 survey.

Participants randomized to the ITW condition will be provided with a link to the intervention website, which they will be free to access any time throughout their study participation. To promote usage of the website, the modules of the ITW will be available to participants on a staggered basis using event- and time-based triggers. Specifically, an initial set of modules will be available to participants immediately. Once those modules have been completed (which we anticipate will take participants no longer than 2 weeks), a final module will be introduced after one week. This approach of introducing website intervention content in a staggered manner has been shown to facilitate greater use of, and exposure to, health promotion websites (Brouwer et al., 2011). We anticipate that each module will take from 30–40 minutes to complete, although participants will be encouraged to review each module regularly. Key elements of the ITW will be available (for example, as fully formatted .pdf documents) for participants to download and print.

Participants randomized to the Usual Care condition will receive no additional intervention aside from their usual non-study care. At the end of their participation in the study, participants in the Usual Care group will be offered the ITW intervention.

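### Aim 3 lists evaluation and usage of the website as moderators, but both arise only after randomisation and only in the ITW arm, so neither can be identified as a moderator of the randomised effect

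*Combined protocol and SAP*

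**What the plan says.** The list in Section 5.3 has ten entries, and the last names two variables. All share one method: "and evaluation and usage of the ITW. To examine this aim, we will incorporate interactions between the effect of intervention and potential moderators". The Aim 3 statement at the front of the protocol ends its list the same way: "worry about recurrence, and evaluation and usage of the ITW". Section 5.3 sets the outcome times as "with the outcomes at 24 weeks as the primary focus (and 8 week and 48 week outcomes examined secondarily". It removes low-variability candidates, applies Hochberg's procedure to the rest, and uses imputation for dropout.

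Section 3.2 places randomisation directly after the baseline survey. The ITW arm then receives the website link, "which they will be free to access any time throughout their study participation". For Usual Care: "Participants randomized to the Usual Care condition will receive no additional intervention aside from their usual non-study care". Later access is described thus: "At the end of their participation in the study, participants in the Usual Care group will be offered the ITW intervention".

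Table 1 (Section 4.2) schedules evaluation at FU 1 only and website usage at FU 1, FU 2 and FU 3, with neither at baseline. Section 4.2.3 takes usage from the study web server, and its questionnaires ask about the ITW. Section 3.6 says of this aim: "We did not conduct power calculations for Aim 3 because it is an exploratory aim".

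No section says how the two variables would be coded in Usual Care, or plans another analysis relating them to outcome. The other uses of website data in Section 5.3 are descriptive, or compare usage by income and education.

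**The concern.** A treatment-by-moderator interaction compares the treatment effect between levels of a characteristic. Each arm must therefore contain people at those levels, and the characteristic should not itself result from treatment. The other nine listed factors meet this, because Table 1 has a baseline measure for each. Usage and evaluation do not.

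What is at stake is the label on a result. Patients keener to examine their skin may also use the site more and rate it more highly. A slope on usage within the ITW arm could then be reported as evidence that the randomised effect depends on usage, when it partly or wholly reflects who chose to use the site. For thorough SSE there is a further difficulty: one usage measure in Section 4.2.3 is the number of monthly self-checks completed on the site. This may overlap with the outcome, although the documents do not establish that a site check meets the outcome definition.

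**Working it through.** The plan gives no figure for Aim 3, so there is none to reproduce. The expected number of 24-week completers in Section 3.6 checks: 420 × 0.90 = 378, or 210 × 0.90 = 189 per arm if retention is equal (assumption).

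**1. Usage.** Let T = 1 for ITW and 0 for Usual Care, and let U be usage, with U = 0 whenever T = 0.
- Then T·U = U for everyone, so the columns {1, T, U, T·U} contain a duplicate: rank 3 of 4.
- Another constant code c in Usual Care does not help, since U = c(1 − T) + T·U is still a combination of the other columns.
- A baseline moderator with 189 per arm gives rank 4 of 4.

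**2. Evaluation.** E is undefined in Usual Care, so complete cases are ITW only. T is then 1 throughout and duplicates the intercept, and T·E duplicates E. The columns {1, T, E, T·E} have rank 2 of 4, and no treatment contrast remains.

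**3. The reduced model.** {1, T, T·U} has rank 3 of 3 and can be fitted. Its mean is b0 in Usual Care and b0 + b1 + b2·U in ITW, so b2 is a slope on usage among ITW participants.

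Usual Care data can still shift b2 in the planned models. In arbitrary simulated data (189 per arm, three visits, some dropout, GEE, no baseline covariate), only the Usual Care outcomes were replaced:

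| Model | b2 before | b2 after |
|---|---|---|
| Shared time effects, independence | −0.0151 | −0.0213 |
| Arm-specific time, exchangeable | −0.0161 | −0.0151 |
| Arm-specific time, independence | −0.0148 | −0.0148 |

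The values mean nothing in themselves; only whether they move matters. Shared covariates, or a pooled dropout-weight model, can act in the same way. None of these routes brings in information on usage, because nobody in Usual Care has any.

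**4. Confounding without moderation (illustration).** Take a constant effect of 0.4 on the sun protection index (3.4 − 3.0 in Section 3.6), SD 0.76, 189 per arm, no effect modification and no baseline adjustment. Let r be the correlation between usage propensity and untreated outcome. The expected slope per SD of usage is 0.76 × r. The documents give no value for r, so a range is shown (2,000 runs each, nominal two-sided 5% test of b2):

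| r (assumed) | 0.76 × r | Rejected |
|---|---|---|
| 0 | 0 | 6% |
| 0.04 | 0.030 | 10% |
| 0.09 | 0.068 | 23% |
| 0.25 | 0.19 | 93% |

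**5. Timing, with surveys on schedule (assumption).** Section 4.2.2 defines primary thorough SSE over the past 2 months, while the 24-week survey asks about checking over 4 months.
- 2 months = 2 × 365.25/12/7 = 8.70 weeks. For the 24-week outcome the window opens at 24 − 8.70 = week 15.3. For the 8-week outcome, 8 − 8.70 = −0.7, so it covers all the time since baseline.
- 4 months = 17.39 weeks, so the 24-week recall for the number of SSEs opens at 24 − 17.39 = week 6.6.
- Usage counted to week 8 ends 15.3 − 8 = 7.3 weeks before the first of these windows opens, but overlaps the second by 8 − 6.6 = 1.4 weeks.
- Section 4.2.2 states no recall period for the sun protection index.

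**6. Multiplicity.** With one test per factor and α = 0.05 (assumptions), the smallest Hochberg threshold moves from 0.05/11 = 0.0045 to 0.05/9 = 0.0056 once the two are removed.

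**The case against.** The strongest reply is that the aim is exploratory, that software will fit a treatment-by-usage term, and that readers will understand it as a dose-response description. The first two parts are true. But Section 5.3 calls the analysis moderation and groups these variables with nine baseline factors under one test family. Exploratory status does not supply the missing comparison.

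Other replies are weaker. Table 1 does not mark the two rows as ITW only, but this follows from Sections 3.2 and 4.2.3. The low-variability rule looks at spread in the sample, and usage may vary widely. Imputation addresses dropout, whereas evaluation in Usual Care is undefined, not missing. Methods for latent usage, such as principal stratification, exist under extra assumptions, but none is planned.

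A reader might infer three stronger things that the documents do not support:
- **That no term can be estimated, or that Usual Care data are irrelevant to it.** The reduced model is fittable, and in repeated-measures GEE models Usual Care outcomes can change its coefficient. What fails is its reading as effect moderation.
- **That the plan would relate usage up to week 48 to the 24-week outcome.** Table 1 lists usage separately at each follow-up, so pairing it by wave is the natural reading. Section 5.3 sets no window, so later usage is a possible misuse, not a proposed analysis.
- **That a week-8 cutoff is clear of the 24-week SSE data in general.** It is clear only of the 2-month primary definition. It would also drop most of the monthly self-checks made before week 24.

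**Conclusion.** The concern holds in this form: as written, Section 5.3 tests two variables as moderators that cannot be identified as such, and any term actually fitted would reflect in essence a non-randomised association within the ITW arm. The rank results rest only on Usual Care having no website access during follow-up, which Section 3.2 states. How large any confounding would be is unknown, and the rejection rates above are illustrations at assumed correlations.

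The scope is small: one of ten listed entries, covering two variables, though Section 4.2.3 gives several measures of each and so the number of tests could be larger. Nothing here bears on the primary comparison, the mediation analysis or the planned 420 participants. It merits correction because the analysis is wrong as written and the remedy is cheap.

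**What to change.** In the Aim 3 statement and Section 5.3:
- Remove evaluation and usage from the moderators tested by interaction and from the Hochberg family.
- Report both within the ITW arm only, labelled as non-randomised associations and adjusted for the baseline value of the outcome and demographics. State that this adjustment does not remove confounding by motivation.
- Pre-specify, for each outcome, a usage window that ends before the period to which the outcome refers. Usage to week 8 is one option for 24-week primary thorough SSE. It covers the staggered release ("which we anticipate will take participants no longer than 2 weeks), a final module will be introduced after one week", so about 2 + 1 = 3 weeks), but it does not suit the number of SSEs at 24 weeks.
- Do not treat the FU 1 evaluation as preceding the 8-week outcome, since both come from the same survey.
- For SSE, report the site self-check count separately from the other usage measures.

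The cost is wording. The data are already to be collected, although a cutoff between surveys assumes dated server records. The sponsor can no longer describe usage or evaluation as moderating the randomised effect, and usage after the chosen window is left out of the association.
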